11.5. Pharmacodynamic Analyses

Pharmacodynamic evaluable population will be used for PD analyses. The BTK and ITK binding site occupancy will be tabulated and summarized at each timepoint using descriptive statistics (mean, SD, coefficient of variation, median, minimum and maximum). Additional analyses (eg, subgroup analyses by ibrutinib dose or concomitant CYP3A inhibitors) may be performed as deemed necessary.

11.6. Pharmacokinetic/Pharmacodynamic Analyses

Relationships between PK of ibrutinib and PD measures may be explored as deemed necessary.

11.7. Safety Analyses

Safety population will be used for safety analyses. The safety parameters to be evaluated are the incidence, intensity, relationship to study drug, action taken with regards to the study drug, and type of adverse events, vital signs measurements, and clinical laboratory results in the safety population. Exposure to and reasons for discontinuation from study treatment will be tabulated in the all treated population.

Adverse Events

The verbatim terms used in the CRF by investigators to identify adverse events will be coded using the Medical Dictionary for Regulatory Activities (MedDRA). All reported adverse events will be included in the analysis. Treatment-emergent adverse events are adverse events with onset during the treatment phase or that are a consequence of a preexisting condition that has worsened since baseline, and occur during treatment or within 30 days following the last dose of study treatment, or any adverse event that is considered study treatment-related regardless of the start date of the event. The number and percent of subjects with treatment-emergent adverse events will be summarized according to intensity using the NCI-CTCAE (Version 4.03), drug relationship, and outcome. For each adverse event, the percentage of subjects who experience at least 1 occurrence of the given event will be summarized. Summaries, listings, datasets, or

subject narratives may be provided, as appropriate, for those subjects who die, who discontinue study drug due to an adverse event, or who experience a severe or an SAE.

Clinical Laboratory Tests

Laboratory data will be summarized by type of laboratory test. Reference ranges and markedly abnormal results (specified in the Statistical Analysis Plan) will be used in the summary of laboratory data. Descriptive statistics will be calculated for each laboratory analyte at baseline and for observed values and changes from baseline at each scheduled timepoint. Frequency tabulations of the changes from baseline results will be presented in pre versus postintervention cross-tabulations (with classes for below, within, and above normal ranges). Frequency tabulations of the abnormalities will be made. A listing of subjects with any laboratory results outside the reference ranges will be provided. A listing of subjects with any markedly abnormal laboratory results will also be provided.

Parameters with predefined NCI-CTCAE toxicity grades will be summarized. Change from baseline to the worst adverse event grade experienced by the subject during the study will be provided as shift tables.

Vital Signs

Descriptive statistics of temperature, pulse rate, respiratory rate, and blood pressure (systolic and diastolic) supine values and changes from baseline will be summarized at each scheduled timepoint. The percentage of subjects with values beyond clinically important limits will be summarized.

12. ADVERSE EVENT REPORTING

Timely, accurate, and complete reporting and analysis of safety information from clinical studies are crucial for the protection of subjects, investigators, and the sponsor, and are mandated by regulatory agencies worldwide. The sponsor has established Standard Operating Procedures in conformity with regulatory requirements worldwide to ensure appropriate reporting of safety information; all clinical studies conducted by the sponsor or its affiliates will be conducted in accordance with those procedures.

Method of Detecting Adverse Events and Serious Adverse Events

Care will be taken not to introduce bias when detecting AEs or SAEs. Open-ended and nonleading verbal questioning of the subject is the preferred method to inquire about adverse event occurrence.

12.1. Definitions

12.1.1. Adverse Event Definitions and Classifications

Adverse Event

An adverse event is any untoward medical occurrence in a clinical study subject administered a medicinal (investigational or non-investigational) product. An adverse event does not necessarily

have a causal relationship with the intervention. An adverse event can therefore be any unfavorable and unintended sign (including an abnormal finding), symptom, or disease temporally associated with the use of a medicinal (investigational or non-investigational) product, whether or not related to that medicinal (investigational or non-investigational) product. (Definition per International Conference on Harmonisation [ICH]).

This includes any occurrence that is new in onset or aggravated in severity or frequency from the baseline condition, or abnormal results of diagnostic procedures, including laboratory test abnormalities.

Note: The sponsor collects adverse events starting with the signing of the ICF (refer to Section [12.3.1](#), All Adverse Events, for time of last adverse event recording).

Serious Adverse Event

An SAE based on ICH and European Union Guidelines on Pharmacovigilance for Medicinal Products for Human Use is any untoward medical occurrence that at any dose:

- Results in death
- Is life-threatening
(The subject was at risk of death at the time of the event. It does not refer to an event that hypothetically might have caused death if it were more severe)
- Requires inpatient hospitalization or prolongation of existing hospitalization
- Results in persistent or significant disability/incapacity
- Is a congenital anomaly/birth defect
- Is a suspected transmission of any infectious agent via a medicinal product
- Is Medically Important*

*Medical and scientific judgment should be exercised in deciding whether expedited reporting is also appropriate in other situations, such as important medical events that may not be immediately life threatening or result in death or hospitalization but may jeopardize the subject or may require intervention to prevent one of the other outcomes listed in the definition above. These should usually be considered serious.

If a serious and unexpected adverse event occurs for which there is evidence suggesting a causal relationship between the study drug and the event (eg, death from anaphylaxis), the event must be reported as a serious and unexpected suspected adverse reaction even if it is a component of the study endpoint (eg, all-cause mortality), other than progression of cGVHD.

Unlisted (Unexpected) Adverse Event/Reference Safety Information

An adverse event is considered unlisted if the nature or severity is not consistent with the applicable product reference safety information. For ibrutinib, the expectedness of an adverse event will be determined by whether or not it is listed in the IB.

Adverse Event Associated With the Use of the Intervention

An adverse event is considered associated with the use of the intervention if the attribution is possible, probable, or very likely by the definitions listed in Section 12.1.2, Attribution Definitions.

12.1.2. Attribution Definitions

Not Related

An adverse event that is not related to the use of the intervention.

Doubtful

An adverse event for which an alternative explanation is more likely, eg, concomitant drug(s), concomitant disease(s), or the relationship in time suggests that a causal relationship is unlikely.

Possible

An adverse event that might be due to the use of the intervention. An alternative explanation, eg, concomitant drug(s), concomitant disease(s), is inconclusive. The relationship in time is reasonable; therefore, the causal relationship cannot be excluded.

Probable

An adverse event that might be due to the use of the intervention. The relationship in time is suggestive (eg, confirmed by dechallenge). An alternative explanation is less likely, eg, concomitant drug(s), concomitant disease(s).

Very Likely

An adverse event that is listed as a possible adverse reaction and cannot be reasonably explained by an alternative explanation, eg, concomitant drug(s), concomitant disease(s). The relationship in time is very suggestive (eg, it is confirmed by dechallenge and rechallenge).

12.1.3. Severity Criteria

An assessment of severity grade will be made using the NCI-CTCAE Version 4.03. The investigator should use clinical judgment in assessing the severity of events not directly experienced by the subject (eg, laboratory abnormalities).

12.2. Special Reporting Situations

Safety events of interest on a sponsor study drug that may require expedited reporting or safety evaluation include, but are not limited to:

- Overdose of a sponsor study drug
- Suspected abuse/misuse of a sponsor study intervention
- Accidental or occupational exposure to a sponsor study drug

- Medication error involving a sponsor product (with or without subject/patient exposure to the sponsor study drug, eg, name confusion)
- Exposure to a sponsor study drug from breastfeeding

Special reporting situations should be recorded in the CRF. Any special reporting situation that meets the criteria of an SAE should be recorded on the SAE page of the CRF.

12.3. Procedures

12.3.1. All Adverse Events

All adverse events and special reporting situations, whether serious or nonserious, will be reported from the time a signed and dated ICF is obtained until 30 days after the last dose of ibrutinib, or the start of subsequent cGVHD treatment, if earlier. Adverse events reported after 30 days following the last dose of ibrutinib or the time of starting the subsequent systemic treatment for cGVHD should also be reported if considered related to ibrutinib. Resolution information after 30 days should be provided, if it can be obtained. All Grade 3 or Grade 4 adverse events considered related to ibrutinib must be followed until recovery to baseline or Grade ≤ 1 or until no further improvement is expected. Cardiac adverse events of Grade 2 or higher will be followed until improvement to baseline or Grade ≤ 1 or until no further improvement is expected. The unresolved aforementioned events will be followed for a maximum of 24 weeks. All adverse events of special interest as defined in Section 12.3.3 related to bleeding or resulting in bleeding complications must be followed until recovery or until there is no further improvement. Serious adverse events, including those spontaneously reported to the investigator within 30 days after the last dose of ibrutinib, must be reported using the Serious Adverse Event Form. The sponsor will evaluate any safety information that is spontaneously reported by an investigator beyond the time frame specified in the protocol.

Progressive disease of cGVHD should not be reported as an adverse event, but symptoms/clinical signs in a patient with disease progression may be reported (see Section 12.3.2). Otherwise, all events that meet the definition of an SAE will be reported as SAEs, regardless of whether they are protocol-specific assessments.

All adverse events, regardless of seriousness, severity, or presumed relationship to study drug, must be recorded using medical terminology in the source document and the CRF. Whenever possible, diagnoses should be given when signs and symptoms are due to a common etiology (eg, cough, runny nose, sneezing, sore throat, and head congestion should be reported as "upper respiratory infection"). Investigators must record in the CRF their opinion concerning the relationship of the adverse event to study therapy. All measures required for adverse event management must be recorded in the source document and reported according to sponsor instructions.

The sponsor assumes responsibility for appropriate reporting of adverse events to the regulatory authorities. The sponsor will also report to the investigator (and the head of the investigational institute where required) all suspected unexpected serious adverse reactions (SUSARs). The investigator (or sponsor where required) must report SUSARs to the appropriate Independent

Ethics Committee/Institutional Review Board (IEC/IRB) that approved the protocol unless otherwise required and documented by the IEC/IRB.

For all studies with an outpatient phase, including open-label studies, the subject must be provided with a "wallet (study) card" and instructed to carry this card with them for the duration of the study indicating the following:

- Study number
- Statement, in the local language(s), that the subject is participating in a clinical study
- Investigator's name and 24-hour contact telephone number
- Local sponsor's name and 24-hour contact telephone number (for medical staff only)
- Site number
- Subject number

12.3.2. Serious Adverse Events

All SAEs occurring during the study must be reported to the appropriate sponsor contact person by study-site personnel within 24 hours of their knowledge of the event.

Information regarding SAEs will be transmitted to the sponsor using the Serious Adverse Event Form and Safety Report Form of the CRF, which must be completed and reviewed by a physician from the study site, and transmitted to the sponsor within 24 hours. The initial and follow-up reports of an SAE should be transmitted electronically or by facsimile (fax).

All SAEs that have not resolved by the end of the study, or that have not resolved upon discontinuation of the subject's participation in the study, must be followed until any of the following occurs:

- The event resolves
- The event stabilizes
- The event returns to baseline, if a baseline value/status is available
- The event can be attributed to agents other than the study drug or to factors unrelated to study conduct
- It becomes unlikely that any additional information can be obtained (subject or health care practitioner refusal to provide additional information, lost to follow-up after demonstration of due diligence with follow-up efforts)

Suspected transmission of an infectious agent by a medicinal product will be reported as an SAE. Any event requiring hospitalization (or prolongation of hospitalization) that occurs during the course of a subject's participation in a study must be reported as an SAE, except hospitalizations for the following:

- Hospitalizations not intended to treat an acute illness or AE (eg, social reasons such as pending placement in long-term care facility).

- Surgery or procedure planned before entry into the study (must be documented in the CRF). Note: Hospitalizations that were planned before the signing of the ICF, and where the underlying condition for which the hospitalization was planned has not worsened, will not be considered SAEs. Any AE that results in a prolongation of the originally planned hospitalization is to be reported as a new SAE.
- For convenience the investigator may choose to hospitalize the subject for the duration of the intervention period.
- The administration of blood or platelet transfusion. Hospitalization or prolonged hospitalization for a complication of such transfusion remains a reportable SAE.

Progression of the disease under study is not considered an adverse event (or SAE), even if it results in death during the AE reporting period. If a clinical sign or symptom or a laboratory test abnormality is observed in a patient with disease progression, but is not related to progression of the disease under study, then the usual AE reporting requirements apply.

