1.4.3. Risks

Cardiac Arrhythmias

Atrial fibrillation, atrial flutter, and cases of ventricular tachyarrhythmia including some fatal events, have been reported in subjects treated with ibrutinib, particularly in subjects with cardiac risk factors, hypertension, acute infections, and a previous history of cardiac arrhythmia. Periodically monitor subjects clinically for cardiac arrhythmia. Subjects who develop arrhythmic symptoms (eg, palpitations, lightheadedness, syncope, chest discomfort or new onset dyspnea) should be evaluated clinically, and if indicated, have an electrocardiogram (ECG) performed. For cardiac arrhythmias which persist, consider the risks and benefits of ibrutinib treatment, and follow the dose modification guidelines.

Bleeding-related Events

There have been reports of hemorrhagic events in subjects treated with ibrutinib, both with and without thrombocytopenia. These include minor hemorrhagic events such as contusion, epistaxis, and petechiae; and major hemorrhagic events, some fatal, including gastrointestinal (GI) bleeding, subdural intracranial hemorrhage, and hematuria. Use of ibrutinib in subjects requiring anticoagulants or medications that inhibit platelet function may increase the risk of bleeding. Subjects with congenital bleeding diathesis have not been studied. In an in vitro platelet function study, inhibitory effects of ibrutinib on collagen induced platelet aggregation were observed.

Cytopenias

Treatment-emergent Grade 3 or 4 cytopenias (neutropenia, thrombocytopenia, and anemia) were reported in subjects treated with ibrutinib. Subjects should be monitored for fever, weakness, or easy bruising and/or bleeding.

Diarrhea

Diarrhea is the most frequently reported nonhematologic AE with ibrutinib monotherapy and combination therapy. Other frequently reported GI events include nausea, vomiting, and constipation. These events are rarely severe. Should symptoms be severe or prolonged, ibrutinib should be considered to follow dose modification guidelines (see Section 6.1.1).

Infections

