 - a. Absolute neutrophil count (ANC) $\geq 1,000/\mu\text{L}$ and off growth factor support in 7 days prior the laboratory test
 - b. Platelets $\geq 30,000/\mu\text{L}$ and no transfusion support in 7 days prior the laboratory test
 - c. Hemoglobin ≥ 8 g/dL and no transfusion or growth support in 7 days prior the laboratory test
9. Prothrombin time (PT)/international normalized ratio (INR) $<1.5 \times$ ULN and partial thromboplastin time (PTT) (activated PTT [aPTT]) $<1.5 \times$ ULN (unless abnormalities are unrelated to coagulopathy or bleeding disorder).
10. Must sign an informed consent form (ICF) (or their legally acceptable representative must sign) indicating that he or she understands the purpose of, and procedures required for, the study and is willing to participate in the study. Assent is also required of children capable of understanding the nature of the study.
11. History of allo-HCT for underlying hematological disease.
12. A woman of childbearing potential must have a negative highly sensitive serum (β -human chorionic gonadotropin [β -hCG]) at screening and a negative urine pregnancy test at Day 1 prior to first dose of ibrutinib.
13. Before the first dose of ibrutinib, a woman must be either:
 - a. Not of childbearing potential defined as:
 - postmenopausalA postmenopausal state is defined as no menses for 12 months without an

alternative medical cause.

- permanently sterile

Permanent sterilization methods include hysterectomy, bilateral salpingectomy, bilateral tubal occlusion/ligation procedures, and bilateral oophorectomy.

b. Of childbearing potential* and

- practicing a highly effective method of contraception (failure rate of <1% per year when used consistently and correctly).

Examples of highly effective contraceptives include:

intrauterine device (IUD); intrauterine hormone-releasing system (IUS); vasectomized partner; sexual abstinence; combined (estrogen- and progestogen-containing) oral hormonal contraception

- agrees to remain on a highly effective method throughout the study and for at least 1 month after the last dose of ibrutinib.

*In this study, a premenarchal (defined as menarche has not yet occurred) woman is considered as having childbearing potential because menarche might occur during the study.

14. A woman must agree not to donate eggs (ova, oocytes) for the purposes of assisted reproduction during the study and for at least 1 month after receiving the last dose of ibrutinib.

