12.3.3. Adverse Events of Special Interest

Specific adverse events, or groups of adverse events, will be followed as part of standard safety monitoring activities by the sponsor. These events, meeting the definition of major hemorrhage listed below, will be reported to the sponsor within 24 hours of awareness irrespective of seriousness (ie, serious and nonserious AEs) following the procedure described above for SAEs and will require enhanced data collection.

Major hemorrhage is defined as:

- Any treatment-emergent hemorrhagic adverse event of Grade 3 or higher. All hemorrhagic events requiring a transfusion of red blood cells should be reported as Grade 3 or higher adverse events per NCI-CTCAE.
- Any treatment-emergent SAE of bleeding of any grade.
- Any treatment-emergent central nervous system hemorrhage/hematoma of any grade.

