#### **Major hemorrhage**

Major hemorrhage is defined as:

- Treatment-emergent hemorrhagic adverse event of Grade 3 or higher. All hemorrhagic events requiring a transfusion of red blood cells should be reported as Grade 3 or higher adverse events per NCI-CTCAE.
- Treatment-emergent SAE of Hemorrhagic event of any grade
- Treatment-emergent central nervous system hemorrhage/hematoma of any grade

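### Section 12.3.2 exempts hospitalization for transfusion from SAE reporting without limit on cause, which conflicts with Sections 12.1.1 and 12.3.1 and can leave a treatment-emergent cytopenia or bleed out of the SAE data when that admission is its only seriousness criterion

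*Protocol*

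**What the plan says.** Protocol Section 12.1.1 defines an SAE by a list of criteria. One is "Requires inpatient hospitalization or prolongation of existing hospitalization", with no exception for transfusion. Section 12.3.1 adds that, apart from progression of cGVHD itself, events meeting the SAE definition are to be reported as SAEs.

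Section 12.3.2 says that any event requiring hospitalization "must be reported as an SAE, except hospitalizations for the following", and then gives four exceptions. The last is "The administration of blood or platelet transfusion. Hospitalization or prolonged hospitalization for a complication of such transfusion remains a reportable SAE".

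Section 12.3.3 defines major hemorrhage by three alternative criteria: a treatment-emergent hemorrhagic event of Grade 3 or higher (a bleed needing red cells is to be reported at that grade), "Any treatment-emergent SAE of bleeding of any grade", and CNS hemorrhage of any grade. Major hemorrhage goes to the sponsor within 24 hours whether serious or not. SAP Section 6.1.1 repeats the three criteria, the second as "Treatment-emergent SAE of Hemorrhagic event of any grade". SAP Section 6.1 plans a table of serious TEAEs and a listing of SAEs.

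**The concern.** The transfusion exception is worded by what was given during the stay. It does not ask why the transfusion was needed. Only a complication of the transfusion is brought back into reporting, which implies that the event leading to the transfusion stays exempt.

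That matters because the events that lead to transfusion are named risks of the drug. Section 1.4.3 describes major hemorrhagic events, some fatal, and says "Treatment-emergent Grade 3 or 4 cytopenias (neutropenia, thrombocytopenia, and anemia) were reported in subjects treated with ibrutinib". Inclusion criterion 8 requires, for platelets, "no transfusion support in 7 days prior the laboratory test", and has a similar rule for hemoglobin. A transfusion admission on study may therefore reflect a new or worsened event.

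If such an event is not classed as serious, there is no 24-hour SAE report, it cannot be assessed as a SUSAR, and it is missing from the Serious TEAE table and the SAE listing. In a multicenter study, two sites could classify the same admission differently, each with support from the protocol. Safety is a stated secondary objective.

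**Working it through.** The plan gives no figure on this point to reproduce, so the check is mainly a comparison of texts.

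**Step 1: is the exception limited by its context?** The neighbouring entries in Section 12.3.2 show how a limit would be written. One covers "Hospitalizations not intended to treat an acute illness or AE". The next covers a procedure planned before study entry; its note, on stays planned before the ICF was signed, requires that the underlying condition has not worsened. The transfusion entry has neither limit. Read literally, it covers an unplanned admission for a treatment-emergent event.

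**Step 2: do the sections agree?** Take a treatment-emergent event whose only seriousness criterion is an admission to transfuse. Under Sections 12.1.1 and 12.3.1 it is an SAE and is reported as one. Under Section 12.3.2 the admission is exempt. The protocol does not say which section prevails.

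**Step 3: what can be lost?** In every row below, admission for transfusion is the only seriousness criterion met.

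| Treatment-emergent event | 12.1.1 and 12.3.1 | 12.3.2 | Major hemorrhage if 12.3.2 is followed |
|---|---|---|---|
| Anemia or thrombocytopenia without bleeding | SAE | Exempt | Not applicable |
| Bleed given red cells | SAE | Exempt | Counted, because it is reported as Grade 3 or higher |
| Bleed of Grade 3 or higher, or CNS bleed | SAE | Exempt | Counted, by grade or site |
| Grade 1-2, non-CNS bleed, transfused without red cells | SAE | Exempt | Missed, because only the SAE criterion could include it |

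The cytopenia row is the main gap, because the rule of 24-hour reporting irrespective of seriousness covers major hemorrhage only. The last row is the whole of the effect on major hemorrhage.

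**Step 4: how much does one subject weigh?** Protocol Section 11.2 and SAP Section 1.4 give N = 17; SAP Section 1.2 mentions approximately 20 enrolled. For one subject whose only SAE is of this kind, the change in SAE incidence is 100 × 1/N:

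- N = 17: 100 × 1/17 = 5.9 percentage points
- N = 20: 100 × 1/20 = 5.0 percentage points

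The documents give no rate of admission for transfusion, so no expected number of such subjects can be derived.

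**The case against.** The strongest reply is that the entry exempts a kind of hospital stay. It does not declare an event nonserious. Death, threat to life, disability and medical importance still apply, and Section 12.1.1 says that medically important events should usually be considered serious. A stay to investigate or control a bleed is not a stay for transfusion. Section 12.3.1 also points towards reporting. All of this stands. A reader might infer that every bleed or cytopenia admitted for transfusion leaves the SAE count; the documents do not support that. What remains is that capture then rests on judgment or on the site's choice of section, where the hospitalization criterion would have settled it.

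The second reply is that the toxicity stays visible, and this also stands. All AEs are recorded whatever their seriousness. SAP Section 6.1 tabulates TEAEs with Grade 3 or higher shown. SAP Section 6.1.1 has a separate Hemorrhagic event AESI, based on the hemorrhage SMQ and not restricted to serious events. SAP Section 6.3 gives worst-grade shift tables, with hemoglobin and platelets among the tests analyzed. What can be lost is the seriousness classification and the expedited report.

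Third, a transfusion on study need not reflect a new event. Entry is allowed with platelets of 30,000/µL and hemoglobin of 8 g/dL, and Attachment 1 lists thrombocytopenia among the features that can accompany cGVHD. That is right, and it is why the exception should separate unworsened pre-existing conditions from treatment-emergent ones.

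Fourth, a reader might assume that up to 3 of 17 subjects are affected and infer a shortfall of up to 17.6 points (3/17). Nothing in the documents supports that count. In the earlier cGVHD study, Protocol Table 3 lists only fatigue and pneumonia as Grade 3 or 4 TEAEs above 10%, so any single cytopenia term was at most 4 of 42 (9.5%), equivalent to 0.095 × 17 = 1.6 subjects, before requiring admission for transfusion alone and no other SAE. Nor can the SAE rate be said to be biased against that study's 52.4%, since the documents do not give its exemption rules.

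**Conclusion.** The point holds as a conflict between Sections 12.1.1, 12.3.1 and 12.3.2 that falls on named risks of the drug. A treatment-emergent anemia, thrombocytopenia or bleed can be left out of 24-hour SAE reporting and the Serious TEAE table if two conditions are met: the site follows Section 12.3.2 literally, and admission for transfusion is the only seriousness criterion. The effect on major hemorrhage is confined to the one narrow class of bleed shown above.

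The weight of one affected subject is 5.9 points of SAE incidence at N=17, provided that subject has no other SAE. How many subjects would be affected is unknown. The primary endpoint and the success criterion are untouched, no interim analysis is planned, and no stopping rule in the documents uses SAE counts. It is worth correcting because the correction is cheap and removes a contradiction in the safety reporting rules.

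**What to change.** Reconcile the three sections by rewording the last exception in Section 12.3.2:

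- Limit it to transfusion planned for a condition that was documented before the ICF was signed and has not worsened, as the planned-procedure entry in the same list already does.
- State that hospitalization, or its prolongation, to transfuse for a treatment-emergent hemorrhage, anemia or thrombocytopenia is a reportable SAE.
- Keep the existing sentence on complications of the transfusion.

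A bleed admitted for transfusion would then meet the SAE criterion for major hemorrhage in Section 12.3.3 and SAP Section 6.1.1 without any change to those definitions. The CRF completion guidelines should carry the same wording so that sites apply one rule.

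The cost is a short text change, a few more SAE forms and a possibly slightly higher SAE rate.
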